**Table 10-1: Phase 3-4 liver chemistry stopping criteria and follow-up assessments**

Liver Chemistry Stopping Criteria	
ALT-absolute	ALT≥8xULN
ALT increase	ALT≥5xULN but <8xULN persists for ≥2 weeks ALT≥3xULN but <5xULN persists for ≥4 weeks
Bilirubina,b	ALT≥3xULN and bilirubin ≥2xULN (>35% direct bilirubin)
INRb	ALT≥3xULN and INR>1.5, if INR measured
Cannot monitor	ALT≥5xULN but <8xULN and cannot be monitored weekly for ≥2 weeks ALT≥3xULN but <5xULN and cannot be monitored weekly for ≥4 weeks
Symptomatic	ALT≥3xULN associated with symptoms (new or worsening) believed to be related to liver injury or hypersensitivity
Suggested Actions and Follow up Assessments	
Actions	

• Immediately discontinue study medication

• Report the event to UCB within 24 hours

• Complete the Liver Event eCRF, and complete an SAE data collection tool if the event also met the criteria for an SAEb

	
Follow-up Assessments	

• Viral hepatitis serologyd

• Obtain INR and recheck with each liver chemistry assessment until the transaminases values show downward trend

	

**Table 10-1: Phase 3-4 liver chemistry stopping criteria and follow-up assessments**

Liver Chemistry Stopping Criteria	

 
• Perform liver chemistry follow-up assessments
 
• Monitor the participant until liver chemistry test abnormalities resolve, stabilize, or return to baseline (see MONITORING)
 
• Do not restart/rechallenge participant with study medication unless allowed per protocol and UCB approval is granted
 
• If restart/rechallenge not allowed per protocol or not granted, permanently discontinue study medication and continue participant in the study for any protocol specified follow up assessmentsConsider the need for a toxicology screening
 
 
MONITORING:
 
For bilirubin or INR criteria
 
 
• Repeat liver chemistry tests (include ALT, AST, alkaline phosphatase, bilirubin) and perform liver event follow-up assessments within 24 hours
 
• Monitor participant twice weekly until liver chemistry test abnormalities resolve, stabilize, or return to baseline
 
• A specialist or hepatology consultation is recommended
 
 
For all other criteria
 
 
• Repeat liver chemistry tests (include ALT, AST, alkaline phosphatase, bilirubin) and perform liver chemistry follow-up assessments within 24 to 72 hours
 
• Monitor participants weekly until liver chemistry abnormalities resolve, stabilize, or return to baseline
 
	
 
• Only in those with underlying chronic hepatitis B at study entry (identified by positive hepatitis B surface antigen), quantitative hepatitis B DNA and hepatitis delta antibodyc
 
• Obtain blood sample for PK analysisa
 
• Serum CPK and LDH
 
• Fractionate bilirubin, if total bilirubin <math>\geq 2 \times \text{ULN}</math>
 
• Obtain complete blood count with differential to assess eosinophilia
 
• Record the appearance or worsening of clinical symptoms of liver injury (eg, fatigue, nausea, vomiting, right upper quadrant pain), or hypersensitivity, on the AE report form
 
• Record use of concomitant medications (including acetaminophen, herbal remedies, and other over-the-counter medications) on the Concomitant Medications eCRF.
 
 
For bilirubin or INR criteria:
 
Anti-nuclear antibody, anti-smooth muscle antibody, Type 1 anti-liver kidney microsomal antibodies, and quantitative total IgG or gamma globulins
 
 
• Serum acetaminophen adduct HPLC assay (quantifies potential acetaminophen contribution to liver injury in participants with definite or likely acetaminophen use in the preceding week [James, 2009])
 
 
NOTE: Not required in China.
 
 
• Liver imaging (ultrasound, magnetic resonance, or computerized tomography) and/or liver biopsy to evaluate liver disease; complete Liver Imaging and/or Liver Biopsy eCRFs
 


AE=adverse event; ALT=alanine aminotransferase; AST=aspartate aminotransferase; CPK=creatine phosphokinase; DNA=deoxyribonucleic acid; eCRF=electronic Case Report Form; HBcAb=hepatitis B core antibody; HBsAg=hepatitis B surface antigen; HPLC=high performance liquid chromatography; IgG=immunoglobulin G; IgM= immunoglobulin M; INR=internal normalized ratio; LDH=lactate dehydrogenase; PCR=polymerase chain reaction; PK=pharmacokinetic; RNA=ribonucleic acid; ULN=upper limit of normal; SAE=serious adverse event

a Serum bilirubin fractionation should be performed if testing is available. If serum bilirubin fractionation is not immediately available, discontinue study medication if ALT  $\geq 3 \times \text{ULN}$  and bilirubin  $\geq 2 \times \text{ULN}$ . Additionally, if

serum bilirubin fractionation testing is unavailable, **record the absence/presence of detectable urinary bilirubin on dipstick** which is indicative of direct bilirubin elevations suggesting liver injury.

b All events of ALT $\geq$ 3xULN and bilirubin $\geq$ 2xULN (>35% direct bilirubin) or ALT $\geq$ 3xULN and INR $>$ 1.5 may indicate severe liver injury (**possible ‘Hy’s Law’**) and **must be reported as an SAE (excluding studies of hepatic impairment or cirrhosis)**. The INR measurement is not required and the stated threshold value will not apply to participants receiving anticoagulants.

c New or worsening symptoms believed to be related to liver injury (such as fatigue, nausea, vomiting, right upper quadrant pain or tenderness, or jaundice) or hypersensitivity (such as fever, rash or eosinophilia).

d Includes: Hepatitis A IgM antibody; HBsAg and HBCAb; hepatitis C RNA; cytomegalovirus IgM antibody; Epstein-Barr viral capsid antigen IgM antibody (or if unavailable, heterophile antibody or monospot testing); and hepatitis E IgM antibody.

e If hepatitis delta antibody assay cannot be performed, it can be replaced with a PCR of hepatitis D RNA virus (where needed) (Le Gal, 2005).

f PK sample may not be required for participants known to be receiving placebo or non-comparator interventions. Record the date/time of the PK blood sample draw and the date/time of the last dose of study medication prior to the PK blood sample draw on the eCRF. If the date or time of the last dose is unclear, provide the participant’s best approximation. If the date/time of the last dose cannot be approximated OR a PK sample cannot be collected in the time period indicated above, do not obtain a PK sample. Instructions for sample handling and shipping are in the Study Reference Manual.

**Table 10-2: Phase 3-4 liver chemistry increased monitoring criteria with continued study medication**

Liver Chemistry Increased Monitoring Criteria	
Criteria	Actions
ALT $\geq$ 5xULN and <8xULN and bilirubin <2xULN without symptoms believed to be related to liver injury or hypersensitivity, and can be monitored weekly for 2 weeks  OR  ALT $\geq$ 3xULN and <5xULN and bilirubin <2xULN without symptoms believed to be related to liver injury or hypersensitivity, and can be monitored weekly for 4 weeks	

Notify the UCB Medical Monitor within 24 hours of learning of the abnormality to discuss study participant safety

Participant can continue study medication

Participant must return weekly for repeat liver chemistry tests (ALT, AST, alkaline phosphatase, bilirubin) until the abnormalities resolve, stabilize, or return to baseline

If at any time, the participant meets liver chemistry stopping criteria, proceed as described in Table 10-1

If ALT decreases from ALT<math>\geq</math>5xULN and <8xULN to <math>\geq</math>3xULN but <5xULN, continue to monitor liver chemistries weekly

If, after 4 weeks of monitoring, ALT <3xULN and bilirubin <2xULN, monitor participants twice monthly until liver chemistry tests resolve, stabilize, or return to baseline

ALT=alanine aminotransferase; AST=aspartate aminotransferase; ULN=upper limit of normal

---

**10.7      Appendix 7: Medical device adverse events, adverse device effects, serious adverse events and device deficiencies: definition and procedures for recording, evaluating, follow-up, and reporting**

Not applicable.

This document cannot be used to support any marketing authorization application and any extensions or variations thereof.

PUBLIC COPY

---

**10.8            Appendix 8: Rapid alert procedures**

Not applicable.

This document cannot be used to support any marketing authorization application and any extensions or variations thereof.  
PUBLIC COPY

---

**10.9        Appendix 9: Country-specific requirements**

Not applicable.

This document cannot be used to support any marketing authorization application and any extensions or variations thereof.  
PUBLIC COPY

## 10.10 Appendix 10: Abbreviations and trademarks

AE	adverse event
AED	antiepileptic drug
ALT	alanine aminotransferase
AST	aspartate aminotransferase
BID	twice per day
C-SSRS	Columbia-Suicide Severity Rating Scale
ECG	electrocardiogram
eCRF	electronic Case Report Form
GCP	Good Clinical Practice
ICF	informed consent form
IEC	Independent Ethics Committee
ICH	International Council for Harmonisation
IMP	investigational medicinal product
IXRS	interactive voice/web response system
LCM	lacosamide
MedDRA	Medical Dictionary for Regulatory Activities®
PK	pharmacokinetic
POS	partial-onset seizures
QTc	corrected QT interval
SAE	serious adverse event
TEAE	treatment-emergent adverse event
ULN	upper limit of normal

This document cannot be used to support any marketing authorization application and any extensions or variations thereof.

## **10.11 Appendix 11: Protocol amendment history**

The Protocol Amendment Summary of Changes Table for the current amendment is located directly before the Table of Contents.

This document cannot be used to support any marketing authorization application and any extensions or variations thereof.  
PUBLIC COPY

1 INTRODUCTION

This Statistical Analysis Plan (SAP) defines the scope of statistical analyses and provides a detailed description of statistical methodology for the statistical analyses to support the final clinical study report for EP0151.

1.1 Objectives and Estimands/Endpoints

Table 1-1: Objectives and Estimands/Endpoints

Objectives	Endpoints
Primary	
Primary Objective: To assess the long-term use of Lacosamide (LCM) oral solution dosed at 2mg/kg/day to 12mg/kg/day when administered to pediatric study participants with epilepsy who have completed EP0034 or SP848	Primary Endpoints: 
• Treatment-emergent adverse events (TEAEs) reported by the study participant or caregiver or observed by the Investigator• Withdrawals from study due to TEAEs• Withdrawals from study due to Serious adverse events (SAEs)• Modal daily dose (mg/kg/day)• Maximum daily dose (mg/kg/day)

1.2 Study design

EP0151 is a multi-center, long-term, open-label, follow-up study to assess the long-term use of LCM oral solution (a formulation suitable for administration to children; also referred to as syrup) for pediatric study participants \leq 6 years of age with epilepsy who have completed either EP0034 or SP848.

Study participants who complete EP0034 or SP848 will be offered participation in EP0151 and will have access to open-label follow-up treatment with LCM. Approximately 80 to 100 study participants are estimated to be eligible for enrollment.

Visit 1 for EP0151 will be the same as Visit 13 in EP0034 or SP848. Clinic visits will be scheduled approximately every 26 weeks relative to the EP0151 Visit 1 date. A visit window of ± 7 days relative to Visit 1 is applicable for all regularly scheduled visits.

All study participants in EP0151 will receive LCM. The Investigator may maintain the study participant's LCM dose from previous studies EP0034 or SP848, decrease the dose in decrements of 2mg/kg/day per week to a minimum dose of LCM 2mg/kg/day, or increase the dose in increments of 2mg/kg/day per week up to a maximum dose of LCM 12mg/kg/day or 600mg/day, whichever is lower, administered twice per day (BID).

This study involves a Treatment Period of approximately up to 205 weeks, depending on the age of the study participant, and an End of Study Period of approximately 8 weeks (including a

Taper Period and a Safety Follow-Up Period). Study participants who reach the end of the study and choose to continue treatment with LCM may be immediately prescribed LCM. The Termination Visit at the end of the Treatment Period will be the last study visit completed for study participants who continue treatment with prescribed LCM. Study participants who choose not to continue with LCM treatment and who are taking a dose of 3mg/kg/day or higher will enter an End of Study Period following completion of the Termination Visit or Early Termination Visit, and will gradually taper from LCM treatment during the Taper Period; a Final Visit will be conducted 30 days after the final dose of LCM.

In situations where provision of LCM oral solution in certain participants >6 years of age (eg, developmental delay, need for more precise dosing as afforded by oral solution formulation, etc.) who may need a longer period of treatment with LCM oral solution, the situation will be assessed for approval by UCB on a case-by-case basis following discussions with the participant's physician.

The end of the study is defined as the date of the last visit of the last study participant in the study.

2 STATISTICAL HYPOTHESES

No statistical hypotheses testing will be conducted in this study.

3 SAMPLE SIZE DETERMINATION

No formal sample size calculations have been performed for this study, as there are no statistical hypotheses being tested. The sample size will be determined by the number of participants in EP0034 or SP848 who have been treated with LCM that are eligible to enter this open-label follow-up study. Approximately 80 to 100 study participants are estimated to be eligible for enrollment.

4 POPULATIONS FOR ANALYSIS

The Safety Set (SS) will consist of all study participants who sign an informed consent form (ICF), and take at least 1 dose of study medication in this study. This analysis set will be used for all safety analyses.

5 STATISTICAL ANALYSES

5.1 General Considerations

Statistical analysis and generation of tables, figures, participant data listings, and statistical output will be performed using SAS Version 9.4 or higher. All tables and listings will use Courier New font size 9.

Descriptive statistics will be displayed to provide an overview of the study results. For categorical parameters, the number and percentage of participants in each category will be presented. The denominator for percentages will be based on the number of participants appropriate for the purpose of analysis. Unless otherwise noted, all percentages will be displayed to 1 decimal place. No percentage will be displayed for zero counts, and no decimal will be presented when the percentage is 100%. For continuous parameters, descriptive statistics will include number of participants (n), mean, standard deviation (SD), median, minimum, and maximum.

Decimal places for descriptive statistics will always apply the following rules:

- “n” will be an integer
- Mean, SD, and median will use 1 additional decimal place compared to the original data
- Minimum and maximum will have the same number of decimal places as the original value

All summaries, unless otherwise stated below, will be presented overall for all participants and additionally based on the participant’s age at time of entry into study EP0151, using the following age groups:

- ≥ 2 to <4 years
- ≥ 4 to <6 years

All summaries will be descriptive; no statistical hypothesis testing is planned.

Only scheduled visits will be included in summaries. A complete set of listings containing all documented data including scheduled and unscheduled and all calculated data (eg, change from Baseline) will be generated, and will be sorted by site, participant number and visit (where applicable). Study participant numbers that were utilized in SP848 and EP0034 will continue to be used in EP0151.

5.1.1 Handling of missing data

5.1.1.1 Missing data

No imputation of missing values for analysis parameters is planned unless otherwise noted. Imputations for missing or partial values for dates for adverse events (AEs) and medications will be applied to determine if they are to be considered treatment-emergent or concomitant, respectively.

With respect to AEs, events with missing intensity will be assumed to be severe. Events with missing relationship to LCM per the investigator will be assumed to be related. Incomplete or missing dates for events will be handled as described in Section 5.1.1.2.

5.1.1.2 Incomplete dates for adverse events and concomitant medications

For analyses of AEs and concomitant medication usage, a complete date must be established in order to correctly identify the AE or medication as occurring during treatment or not. For purposes of imputing missing components of partially-reported start and stop dates for AEs and for medication use, the algorithms listed below will be followed. Start and stop dates of AEs or concomitant medication

will be displayed as reported in the participant data listings (ie, no imputed values will be displayed in data listings).

- Missing start day, but month and year present:

If the start of LCM occurred in the same month and year as the occurrence of the AE/concomitant medication, the start day of the event/concomitant medication will be assigned to the day of first intake of LCM. Otherwise the start day will be set to the 1st day of the month.

- Missing start day and month, but year present:

If the start of LCM occurred in the same year as the occurrence of the AE/concomitant medication, the start day and month will be assigned to the date of first intake of LCM. Otherwise the start day and month will be set to January 1st.

- Missing end day, but month and year present:

The end day will be set to the last day of the month.

- Missing end day and month, but year present:

The end day and month will be set to the latest of the date of Final Visit or the date equivalent to 30 days after last intake of LCM.

However, if the Final Visit year and year for the date which is 30 days after last intake of LCM are greater than the event/concomitant medication year, the day and month are to be set to December 31st.

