5.1.1.4 Incomplete dates for the last administration of LCM

For purposes of imputing missing components of partially reported dates for the last administration of LCM, the algorithms listed below will be followed. Stop dates of LCM will be displayed as reported in the participant data listings (ie, no imputed values will be displayed in data listing).

- Missing last administration day, but month and year present:

The last administration day will be set to the last day of the month or the date of the final contact, whichever is earlier in the month.

- Missing last administration day and month, but year present:

The last administration day will be set to the last day of the year or the date of the final contact, whichever is earlier in the year.

- Completely missing date of last administration:

For calculating the duration of exposure, if the date of last administration is completely missing and no information could be obtained from data cleaning exercises, the date of last administration should be imputed as the date of last contact according to the Study Termination eCRF module. For all other purposes, no imputation will be done if the date of last administration is completely missing.

If a participant died during the study, and the imputed last administration date according to the rules above is after the date of death, the last administration date will be assigned to the date of death.

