5.1.1.5 General imputation rule for incomplete dates

Where necessary for the calculation of derived variables, partial dates will be completed using the earliest calendar date based on the partial date provided. This rule is valid for all partial dates with the exception of the following:

- Start and stop dates of AEs
- Start and stop dates of concomitant medication
- Start and stop dates of LCM

Completely missing dates will not be replaced and the corresponding derived variables will be set to missing.

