5.1.2 General study level definitions

5.1.2.1 Analysis Time Points

5.1.2.1.1 First and last dose of LCM

Unless otherwise noted, all references to the first dose of LCM in this SAP refer to the first dose of LCM during EP0151 (ie, not the first dose of LCM from the previous study in which participants participated prior to EP0151). Unless otherwise noted, all references to the last dose of LCM in this SAP refer to the last dose of LCM in EP0151.

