5.3.1 Definition of endpoints

TEAEs reported by the study participant or caregiver or observed by the Investigator

TEAEs will be defined as those events which started on or after the date of first dose of LCM in EP0151, or events for which severity worsened on or after the date of first dose of LCM in EP0151. AEs which occur within 30 days after final dose of LCM in EP0151 will be considered treatment-emergent.

Withdrawals from study due to TEAEs

Primary reason for premature study termination is collected in eCRF, one of which is AE. Together with the AE information for such participants collected in eCRF, early termination due to TEAE will be derived based on the definition of TEAE.

Withdrawals from study due to SAEs

The premature study termination due to AE collected in eCRF will be further considered for AEs indicated as serious in the eCRF.

Modal daily dose (mg/kg/day)

Definition of modal daily dose is in Section [5.1.2.4](#).

Maximum daily dose (mg/kg/day)

Definition of maximum daily dose is in Section [5.1.2.4](#).

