5.6.2 Adverse Events

AEs will be tabulated by MedDRA system organ class (SOC) and MedDRA preferred term (PT). The number and percentage of participants experiencing each event at least once will be summarized. All summaries will be sorted alphabetically by SOC and by frequency of events within PTs, starting with the most frequent event overall.

AEs will be classified as ongoing at entry, treatment-emergent and post-treatment. Ongoing AEs at entry are defined as AEs which had an onset date prior to the first EP0151 dose of LCM.

TEAEs will be defined as those events which started on or after the date of first dose of LCM in EP0151, or events for which severity worsened on or after the date of first dose of LCM in EP0151. AEs which occur within 30 days after final dose of LCM in EP0151 will be considered treatment-emergent. Post-treatment AEs are defined as AEs which had an onset date after 30 days after the last dose of LCM.

All AEs reported during the study including ongoing AE at entry and post-treatment AEs will be provided in a participant data listing. Ongoing AEs from EP0034 and SP848 will be followed up and reported in this study.

An overview of the incidence of TEAEs will provide the overall summary of TEAEs and the numbers and percentages of participants with at least 1 TEAE, with a serious TEAE, with a drug-related TEAE, with a severe TEAE. The number and percentage of participant discontinuations due to TEAEs, the number and percentage of all deaths (if applicable), and the number and percentage of participants with TEAEs leading to death (if applicable) will also be summarized.

The number and percentage of participants who discontinued due to SAE (regardless of treatment emergent) will also be summarized.

The following summaries of AEs will be provided by MedDRA primary SOC and PT:

- Incidence of TEAEs
- Incidence of serious TEAEs
- Incidence of non-serious TEAEs
- Incidence of ongoing AEs at EP0151 study entry
- Incidence of TEAEs leading to discontinuation
- Incidence of SAEs leading to discontinuation
- Incidence of TEAEs related to potential drug-induced liver injury (PDILI) (defined in

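### Adverse events carried over from the parent study with a partial start date in the year or month of first EP0151 dose are counted as treatment-emergent

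*SAP*

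**What the plan says.** The first primary endpoint in SAP 1.1 is "Treatment-emergent adverse events (TEAEs) reported by the study participant or caregiver or observed by the Investigator". SAP 5.3.1 defines it by date: "TEAEs will be defined as those events which started on or after the date of first dose of LCM in EP0151". Events whose severity worsened on or after that date also count, as do events within 30 days after the final dose. SAP 5.1.2.1.1 fixes the reference point: "all references to the first dose of LCM in this SAP refer to the first dose of LCM during EP0151".

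SAP 5.6.2 brings parent-study events into the data: "Ongoing AEs from EP0034 and SP848 will be followed up and reported in this study". It places them in their own class by onset date only: "Ongoing AEs at entry are defined as AEs which had an onset date prior to the first EP0151 dose of LCM". A separate incidence table is planned for that class.

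SAP 5.1.1.2 gives the rules for partial start dates. If only the year is known and it is the year of first dose, "the start day and month will be assigned to the date of first intake of LCM"; for any other year the start becomes January 1st. If only the day is missing, the start becomes the day of first dose when month and year both match, and otherwise the first of the month. The section has no condition on the stop date or on carry-over from the parent study.

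For AEs with no start date at all, SAP 5.1.1.1 promises imputation for the treatment-emergent decision and refers to 5.1.1.2, which has no such rule. SAP 5.1.1.5 ends: "Completely missing dates will not be replaced and the corresponding derived variables will be set to missing".

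**The concern.** Moving a doubtful onset to the day of first dose is a common convention when the first dose is the child's first exposure. EP0151 is a rollover study: Visit 1 is the parent study's Visit 13, and AEs still open at that visit are carried in. For those events there is no doubt about which side of first dose the onset lies on, whatever part of the date is missing. The rule ignores that knowledge and gives them an onset on Day 1.

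Each such reassignment affects two planned outputs. The event is added to the TEAE summaries and removed from the summary of AEs ongoing at entry. Withdrawals due to TEAEs, another primary endpoint, are derived from the same TEAE definition. The TEAE rate per 100 participant-months counts every TEAE, so it is affected too.

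**Working it through.** The documents give no figure for this point: the study is descriptive and has no formal sample size calculation. The check therefore follows the rules through and then sizes one reassignment.

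**1. The chain of rules.** A carried-over AE is in the EP0151 data (5.6.2). Its class depends on onset against first EP0151 dose (5.6.2, 5.1.2.1.1). If the onset is partial and falls in the year or month of first dose, it is set to the date of first dose (5.1.1.2). An onset on that date satisfies the TEAE definition (5.3.1) and fails the definition of ongoing at entry.

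**2. The rules applied.** Assumed dates, for illustration: first dose 1 July 2021, last dose 1 July 2023.

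| Recorded AE start | Start under 5.1.1.2 | TEAE? |
|---|---|---|
| 2020 | 1 Jan 2020 | no |
| March 2021 | 1 Mar 2021 | no |
| July 2021 | 1 Jul 2021 | yes |
| 2021 | 1 Jul 2021 | yes |
| 2022 | 1 Jan 2022 | yes |
| none | no value given | no rule |

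For an AE carried over from the parent study, the first two rows are classed correctly. The third and fourth are classed wrongly unless severity worsened on or after first dose. The fifth cannot arise, because the onset would be after entry.

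**3. How wide the year-only rule reaches.** The share of the first-dose calendar year that lies before first dose is (days from 1 January to first dose) / 365:

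- 1 February: 31/365 = 8.5%
- 1 April: 90/365 = 24.7%
- 1 July: 181/365 = 49.6%
- 1 October: 273/365 = 74.8%
- 1 December: 334/365 = 91.5%

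The later in the year a child rolls over, the more parent-study time the rule covers.

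**4. Size of one reassignment.** SAP section 3 expects about 80 to 100 participants. One child is 1/100 = 1.0 percentage point or 1/80 = 1.25 points of an incidence. The overall TEAE incidence moves only if that child has no other TEAE; a preferred-term row moves if the child has no other TEAE with that term. The number of children affected is not in the documents. For an assumed 1 to 5 children, the shift is 1 to 5 points (N = 100) or 1.25 to 6.25 points (N = 80). Within the two age groups of SAP 5.1 one child weighs more, but the group sizes are not given.

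**5. AEs with no start date, side by side.**

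- 5.1.1.1: missing as well as partial AE dates will be imputed, under 5.1.1.2.
- 5.1.1.2: a complete date has to be established, but only partial dates have a rule.
- 5.1.1.3: undated medications are classified by their stop date; AEs have no counterpart.
- 5.1.1.5: AE dates are excepted from the partial-date rule, and then completely missing dates are said not to be replaced. Whether that last sentence covers AE dates is not stated.

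No section says how such an AE is classed.

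**The case against.** The strongest defence is that the rule is deliberately conservative: a doubtful onset is counted as on-treatment, just as SAP 5.1.1.1 takes missing intensity as severe and missing relationship as related. That stands for an uncertain onset. It does not reach an event already known, from its carried-over status, to have begun before first dose. The SAP itself uses the stop date to classify undated medications, so such a check fits its own practice.

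Four stronger readings are tempting, and the documents do not support them.

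- **All year-only parent-study AEs become TEAEs.** They do not. Those from earlier calendar years go to January 1st and are classed correctly.
- **Parent-study AEs will often get a start after their own stop.** This is nearly unreachable, because only AEs still ongoing are carried over. It could arise for an AE that began and ended between consent and first dose, which is why a stop-date check is still worth having.
- **Undated AEs drop out of the TEAE tables.** That is one reading of the last sentence of 5.1.1.5. It conflicts with the promise in 5.1.1.1 to impute, and 5.1.1.5 has just listed AE dates as exceptions. The documents show a missing rule, not a rule that discards events, and 5.6.2 lists every AE whatever its class.
- **A missing last-dose date loses TEAEs.** SAP 5.1.1.4 does say "For all other purposes, no imputation will be done if the date of last administration is completely missing". But onset on or after first dose already qualifies an event, and the post-treatment class needs an onset more than 30 days after last dose, which cannot be shown without that date. No lost TEAE follows.

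Two further objections stand. The weight of one child says nothing about how many partial dates there will be. Listings show dates as reported, so a careful reader could trace an affected event.

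**Conclusion.** The point holds for a defined set of events: AEs carried over as ongoing from EP0034 or SP848, with a start known only to the year or month of first EP0151 dose, and with no worsening on or after that dose. SAP 5.1.1.2 and 5.6.2 together count them as TEAEs and remove them from the ongoing-at-entry table, although they are known to precede Day 1. This follows from the stated rules and needs no assumption about the data beyond such a date occurring.

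The direction is an over-count of TEAEs. Each affected child can move an incidence by 1.0 to 1.25 points at the expected enrolment. The number affected cannot be derived from the documents and is probably small. With no hypothesis tests planned, the consequence is the accuracy of descriptive tables for the first primary endpoint and those that depend on it.

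For AEs with no start date, the conclusion is limited to an unfilled cross-reference: 5.1.1.1, 5.1.1.2 and 5.1.1.5 must be reconciled.

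**What to change.** Add two rules to SAP 5.1.1.2.

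1. A partial start date is not moved to first dose when the AE is recorded as ongoing from EP0034 or SP848, or when its stop date is before first dose. Such an AE is classed as pre-dose (ongoing at entry if still ongoing). If its severity worsened on or after first dose it remains a TEAE, as 5.3.1 requires. The class should rest on the carried-over status, not on substituting the parent-study onset date, since that may be the same partial date.
2. An AE with no start date is treatment-emergent unless its stop date is before first dose or it was carried over without worsening. This parallels the medication rule in 5.1.1.3. Align the wording of 5.1.1.1 and 5.1.1.5 with it.

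The cost is a few SAP sentences and minor programming. Carried-over AEs must be identifiable in the data; SAP 5.1 keeps the parent-study participant numbers, which allows linkage if the AE record does not show it. The rules should be written before AEs are classified, so that the class of a primary-endpoint event is not settled case by case.
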